2.6 Analysis of the key secondary objective

There is no key secondary objective.

2.7 Analysis of secondary objectives

All analyses will be based on the FAS unless otherwise specified.

2.7.1 Secondary endpoints

Secondary endpoints include the following:

1. Change from baseline in NT-proBNP at Week 12
2. Change from baseline in echocardiographic measures at Week 12 including:
 - Global longitudinal strain
 - Left atrial volume index
 - Mitral annular E' velocity (Doppler Tissue Imaging)
 - Mitral E/E'
 - LVEF
 - Ventricular-vascular coupling (Ea/Ees)
 - LV end systolic and diastolic volume indices
3. Change in aortic characteristic impedance and change in biomarker levels (BNP, UcGMP and UcGMP to Urinary Creatinine ratio) during both trough and 4 hours post-dose at Week 4

2.7.2 Statistical hypothesis, model, and method of analysis

For NT-proBNP a proportional change from baseline at Week 12 in a logarithmic scale will be analyzed using an ANCOVA model with treatment and the logarithmic baseline biomarker value as explanatory variables. The estimated treatment effect in terms of ratios of geometric means, based on the least squares means from the ANCOVA model, the corresponding two-sided 95% confidence intervals and p-values will be provided.

The change from baseline in the echocardiographic measures at Week 12 will be analyzed using an ANCOVA model with treatment and baseline as explanatory variables.

Correlation coefficients between changes from baseline in aortic characteristic impedance and biomarker levels (BNP, UcGMP and UcGMP to Urinary Creatinine ratio) to Week 4 trough will be calculated by treatment and overall. Corresponding two-sided 95% confidence intervals and p-values will be provided. The same analysis will be conducted on changes in aortic characteristic impedance and biomarker levels from trough to 4 hours post dose at Week 4.

On-treatment analyses of all secondary endpoints will be performed using the same analytical approaches described above.

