## 9.5 Analysis of secondary variables

### 9.5.1 Efficacy variables

1. Change from baseline in NT-proBNP at Week 12
2. Changes from baseline in echocardiographic measures at week 12 including:
  - Global longitudinal strain
  - Left atrial volume index
  - Mitral annular E' velocity (Doppler Tissue Imaging)

- Mitral E/E'
- Left ventricular ejection fraction
- Ventricular-vascular coupling (Ea/Ees)
- LV end systolic and diastolic volume indices

3. The change in aortic characteristic impedance and change in biomarker levels such as BNP, U-cGMP/U-creatinine, during both trough and 4 hours post-dose at Week 4

For NT-proBNP, a proportional change from baseline in a logarithmic scale will be analyzed using an ANCOVA model with treatment and the logarithmic baseline biomarker value as a covariate and baseline (Day 1) as explanatory variables. The estimated treatment effects in terms of ratios of geometric means, based on the least-squared means from the ANCOVA model, the corresponding two-sided 95% confidence intervals and p-values will be provided.

The change from baseline in the echocardiographic measures will be analyzed using an ANCOVA model with treatment and baseline as explanatory variables.

Correlation coefficients between changes from baseline in aortic characteristic impedance and biomarker levels (BNP, U-cGMP/U-creatinine) during both trough and 4 hours post-dose at Week 4 will be calculated by treatment and overall.

For the analysis of secondary efficacy variables, if a subject has no post-baseline value, the missing value will not be imputed and the subject will be removed from the analysis.

Analyses of the secondary efficacy variables will be based on the Full Analysis Set.

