1.1 Study design

This study will use a multicenter, randomized, double-blind, double-dummy, parallel group, active-controlled, forced titration, 12-week design in patients with heart failure and reduced left ventricular ejection fraction (LVEF) $\leq 40\%$. The study duration is a maximum of 30 weeks, including the screening epoch, with 8 scheduled outpatient visits. A total of approximately 432 patients randomized to sacubitril/valsartan or enalapril in a 1:1 ratio is planned with no stratification at approximately 80 centers in the United States.

At the time of randomization, patients will have been on stable treatment with guideline-directed therapy for heart failure with reduced ejection fraction, other than angiotensin converting enzyme inhibitors (ACEi) and angiotensin receptor blockers (ARB), and on an optimal medical regimen to effectively treat co-morbidities such as hypertension, diabetes mellitus and coronary artery disease. All patients will need to meet all other inclusion and none of the exclusion criteria.

Patients will be randomized to either sacubitril/valsartan 24/26 mg bis in diem/twice a day (BID) or enalapril 2.5 mg BID (Dose Level 1), according to the product label(s). Forced titration will occur every 2 weeks to reach the target dose of sacubitril/valsartan 97/103 mg BID or enalapril 10 mg BID (Dose Level 3). Dose level 2 is defined as sacubitril/valsartan 49/51 mg BID or enalapril 5 mg BID. Dose adjustments will only be allowed if indicated per protocol defined safety and tolerability criteria and investigator judgement, or if the investigator believes that adjustment/elimination of concomitant medications is not possible or does not alleviate the side effects of concern. After 12 weeks of double-blind treatment, patients will continue into the 12 week open-label extension.

All patients will need to have a 36-hour washout from study treatment prior to starting the open-label extension to ensure that the blinding of the core study is maintained and to reduce the risk of angioedema. All patients will start open-label treatment on sacubitril/valsartan Dose Level 2, unless they completed double-blind treatment on Dose Level 1. Instead, these patients will enter the open-label extension on sacubitril/valsartan Dose Level 1. Study treatment will be force-titrated every 2 weeks to reach the target dose of sacubitril/valsartan (Dose Level 3).

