2.1 Data analysis general information

 a Novartis-designated Contract Research Organization (CRO) will be performing all analyses outlined in this SAP. SAS[®] version 9.3 (or higher) will be used for all analyses.

Data from all centers that participate in this protocol will be combined, so that an adequate number of patients will be available for analysis.

Unless otherwise specified, for continuous data, the mean, standard deviation, median, first and third quartiles, interquartile range, and minimum and maximum values will be presented. Geometric means and 95% confidence intervals will also be presented for biomarker data. For categorical data, frequencies and percentages will be presented. All statistical tests will be conducted against a two-sided alternative hypothesis, employing a significance level of 0.05.

All data will be provided in listings in addition to summaries described below.

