2.14 Interim analysis

No interim analysis is planned.

3 Sample size calculation

In CHOIR (Mitchell 2002), treatment with Omapatrilat was associated with an approximately ~10% reduction in characteristic impedance at 12 weeks, with little or no change seen amongst enalapril- treated patients. Based on a similar study design and population, and accounting for a dropout rate of 20% from first visit to subsequent follow up and a 10% rate of non-evaluable data, assuming a standard deviation of 80 for the primary efficacy variable and 90% power, a sample size of 432 patients (216 per arm) will be necessary to detect a clinically important change of 30 dyne x sec/cm⁵ between the two treatment groups.

Assuming a significance level of 0.05, a sample size 432 patients would provide 88% power to detect a 25% reduction in the geometric mean of the proportional change from baseline to Week 12 in NT-proBNP for the sacubitril and valsartan treatment group assuming a value of 0.95 for the enalapril group, a value of 0.7125 for the sacubitril and valsartan group (25% reduction), a common standard deviation of 0.85 and a 20% drop-out rate. The difference between the logs for the two treatment groups is therefore assumed to be 0.288.

4 Change to protocol specified analyses

The following changes to protocol specified analyses were made:

- Modified baseline definition as follows:
 - Eliminated requirement that assessment date:time is prior to first dose date:time
 - Clarified how baseline assessments for hemodynamic variables will be identified
- Clarified that tables summarizing demographics and baseline data will be run only on the FAS, and not also on the RS as indicated in the protocol
- Indicated that values of the hemodynamic variable carotid-femoral pulse wave velocity will be negative inverse transformed prior to analysis
- Added separate summaries of prior and concomitant CV, HF, ACEi and ARB medications
- Added the following supportive analyses of the primary endpoint:
 - On-treatment analysis

- Analysis using the “original” aortic characteristic impedance variable
- Analysis using the “alternative” aortic characteristic impedance variable
- Added on-treatment analyses of the secondary endpoints
- Modified the PPS definition to clarify that major protocol deviations will exclude patients from the PPS regardless of the study phase in which they occur
- Added summary of the incidence of hypotension through Week 12

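### SAP 2.7.2: the pooled Zc–biomarker correlation is not adjusted for treatment arm, and neither the biomarker scale nor the type of coefficient is named

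*SAP*

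**What the plan says.** SAP 2.7.2 defines the analysis of objective 3 as "Correlation coefficients between changes from baseline in aortic characteristic impedance and biomarker levels", the biomarkers being BNP, UcGMP and the UcGMP to creatinine ratio; these "to Week 4 trough will be calculated by treatment and overall". Each coefficient gets a two-sided 95% confidence interval and a p-value. The same analysis is repeated for changes from trough to 4 hours post-dose at Week 4. Protocol 9.5.1 has the same by-arm and pooled structure: "during both trough and 4 hours post-dose at Week 4 will be calculated by treatment and overall".

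No adjustment for arm is described for the pooled coefficient. Neither document says whether the coefficient is Pearson or rank-based, or on what scale the biomarker change is taken. For NT-proBNP, the same SAP section is explicit: "a proportional change from baseline at Week 12 in a logarithmic scale will be analyzed". SAP 2.1 adds for biomarkers in general: "Geometric means and 95% confidence intervals will also be presented for biomarker data". On testing it states: "All statistical tests will be conducted against a two-sided alternative hypothesis, employing a significance level of 0.05".

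**The concern.** A correlation computed over two pooled arms has two sources: the relation between the variables inside each arm, and the separation of the arm means on both variables. If treatment moves both Zc and a biomarker, the pooled coefficient is non-zero even when the two are unrelated within each arm. If the shifts run against a true within-arm relation, they hide part of it. A reader of the pooled p-value would take it as evidence that Zc and the biomarker move together in patients, which is the question behind objective 3.

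The missing scale and coefficient type matter for a second reason. A raw change in a skewed biomarker grows with its baseline level, so a few patients with high baselines can dominate a Pearson coefficient. An analysis that yields p-values should have both choices fixed before unblinding.

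**Working it through.** **The plan's own figures (SAP Section 3).** The inputs are a Zc difference of 30 and "assuming a standard deviation of 80 for the primary efficacy variable and 90% power". Per arm, 2 × (1.96 + 1.2816)² × 80² / 30² = 149.4, so 150 (151 with the t distribution). Dividing 151 by 0.70 (20% dropout plus 10% non-evaluable) gives 216 per arm, 432 in total, as stated. For NT-proBNP the log difference is ln(0.95/0.7125) = 0.288. With SD 0.85 and 216 × 0.8 = 172.8 per arm, power is 88.2%, against 88% stated. The plan gives no figure for the objective-3 correlations.

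**Inputs for the pooled coefficient.**
- Zc shift d1 = 30/80 = 0.375 SD. This is the Week 12 planning effect.
- Biomarker shift d2 = 0.288/0.85 = 0.339 SD. This is NT-proBNP at Week 12, used as a proxy because the documents give no effect size for BNP or UcGMP.
- Evaluable N = 432 × 0.70 = 302. With losses multiplied (0.80 × 0.90) it is 311.
- 1:1 allocation, from SAP 1.1: "A total of approximately 432 patients randomized to sacubitril/valsartan or enalapril in a 1:1 ratio is planned with no stratification".

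**Formula.** For equal arms with within-arm correlation r_w:

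pooled r = (r_w + d1·d2/4) / √[(1 + d1²/4)(1 + d2²/4)]

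With r_w = 0 this is 0.0318 / √(1.0352 × 1.0287) = 0.031. By Fisher's z, 0.031 × √299 = 0.53, so the two-sided rejection probability is [1 − Φ(1.43)] + Φ(−2.49) = 8.3% (8.4% at N = 311).

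With half the Zc shift (d1 = 0.1875, an assumption for Week 4), pooled r is 0.0159/1.0187 = 0.016 and rejection is 5.8%.

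Rejection with no within-arm relation, N = 302:

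| Biomarker shift (SD) | Full Week 12 Zc shift | Half that shift |
|---|---|---|
| 0.34 (NT-proBNP proxy) | 8.3% | 5.8% |
| 0.5 (assumed) | 12.1% | 6.8% |
| 1.0 (assumed) | 29.8% | 11.2% |

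A simulation with 155 per arm, 20,000 runs and the full Zc shift gave 8.5%, 12.7% and 31% for the pooled coefficient. The partial correlation adjusted for arm gave 5.0%, 5.2% and 4.8%.

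Masking: with shifts opposed to r_w = 0.20, pooled r is (0.20 − 0.0318)/1.0319 = 0.163 at the proxy shift.

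**Scale, conditional on Pearson with raw changes.** The simulation used a log-normal baseline and a log change with SD 0.85 (borrowed from NT-proBNP). Zc was correlated 0.30 with the log change within arm, with 155 patients per arm. The baseline log-SD is an assumption.

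| Baseline log-SD | Pearson, raw change (power) | Spearman, raw change |
|---|---|---|
| 0.5 | 0.23 (83%) | 0.27 |
| 0.8 | 0.20 (69%) | 0.27 |
| 1.0 | 0.18 (60%) | 0.26 |

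At a log-SD of 1.1, with 151 per arm, Pearson on raw change gives 0.17 (power 54%). Pearson on the log ratio gives 0.30 with power of about 97%.

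**The case against.** **Time point.** The 30/80 Zc effect belongs to Week 12, while objective 3 is read at Week 4. Under Protocol 5.5.4 the target dose level starts only at the Week 4 visit and the morning dose follows the pre-dose assessments, so the Week 4 trough reflects Dose Level 2. Protocol 3.3, which ties a rise in cGMP to neprilysin inhibition, speaks of the target dose. This stands, and it is why the half-shift column is shown.

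**By-arm results.** Coefficients by arm are planned with their own intervals and p-values and are free of the pooling problem. A signal seen only in the pooled figure would be visible as such. This stands too, but it does not correct the pooled p-value that is also reported.

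**Scale.** A reader might infer that raw changes are what the SAP uses. That is the literal reading, but log changes and rank correlation are not excluded. Geometric means are planned in addition to arithmetic summaries, so they do not settle the matter. SAP 2.12 also refers to Section 2.13, which is not in the public text, and nothing can be inferred from its absence.

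**Importance.** A reader might take this for the only mechanistic secondary objective. It is not: objective 2 includes ventricular-vascular coupling, and Protocol 3.2 describes the whole study as a mechanism study. The SAP names no key secondary objective, and the primary test does not depend on these correlations.

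**Trough to 4 hours.** A reader might also infer that this definition was introduced without disclosure. The SAP's amendment history records it as a clarification made before database lock, although Section 4 does not list it.

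**What adjustment does not do.** A partial correlation removes the arm shifts but does not compare the two arms' correlations, which is closer to the wording of objective 3. The by-arm coefficients must therefore stay.

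**Conclusion.** The pooled correlation is unadjusted for arm, and its p-value does not test association alone. At the plan's own effect sizes the inflation is modest: about 8% instead of 5%, and about 6% if the Week 4 Zc shift is half the Week 12 one. Both rest on NT-proBNP as a proxy for the objective-3 biomarkers and on the Week 12 loss rates. The rates of 12% and 30% need biomarker shifts of 0.5 and 1.0 SD, which the documents do not give, and the full Week 12 Zc effect, so they should not be read as expected values. No figure was computed for the trough-to-4-hour change, for which the plan gives no effect size.

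The second defect is an omission: scale and coefficient type are not stated. The attenuation from 0.30 to about 0.17–0.23 applies only if Pearson on raw changes is used, and it rests on assumed baseline log-SDs of 1.1 down to 0.5. A rank coefficient would recover most of it. The point concerns one secondary objective and leaves the primary analysis untouched, but the remedy is nearly free and worth adopting.

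**What to change.** In SAP 2.7.2:
- Correlate the change in Zc with the log ratio of each biomarker, the scale already used for NT-proBNP, and name the coefficient (Pearson, with Spearman as a check).
- Report the pooled result as a partial correlation adjusted for treatment.
- Keep the by-arm coefficients with their intervals.
- Apply the same rules to the trough-to-4-hour analysis.

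The cost is a few lines of SAP text and code, with no new data and no change to the design. The one consequence for interpretation is that the coefficients then refer to proportional, not absolute, biomarker change.

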1.2 Study objectives and endpoints

The primary objective is to determine whether treatment with sacubitril/valsartan provides a superior effect on aortic characteristic impedance compared to enalapril in patients with heart failure and reduced ejection fraction (LVEF $\leq 40\%$) after 12 weeks of treatment. The primary endpoint is the change in aortic characteristic impedance ($Z_c = dP/dQ$ in early systole) between baseline and Week 12.

The secondary objectives are:

1. To evaluate the effect of sacubitril/valsartan vs. enalapril after 12 weeks of treatment on change from baseline in N-terminal Prohormone of B-type Natriuretic Peptide (NT-proBNP).
2. To evaluate the effect of sacubitril/valsartan vs. enalapril after 12 weeks of treatment on the changes from baseline in echocardiographic measures including:
 - a. Global longitudinal strain
 - b. Left atrial volume index
 - c. Mitral annular E' velocity (Doppler Tissue Imaging)
 - d. Mitral E/E'
 - e. LVEF
 - f. Ventricular-vascular coupling (Ea/Es)
 - g. LV end systolic and diastolic volume indices
3. To evaluate the effect of sacubitril/valsartan vs. enalapril after 4 weeks of treatment on the relation between the change in aortic characteristic impedance and change in biomarker levels, including B-type Natriuretic Peptide (BNP) and Urine-cyclic Guanosine Monophosphate (U-cGMP)/U-creatinine, during both trough and 4 hours post-dose.

2 Statistical methods

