2.7.3 Handling of missing values/censoring/discontinuations

For the analysis of secondary endpoints, if a patient has no post-baseline value at the given time point (Week 4 or Week 12), the missing value will not be imputed and the patient will be removed from the analysis.

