2.12 Biomarkers

Biomarkers related to heart failure or mechanism of action (NT-proBNP, BNP, [REDACTED]) and spot urine samples for urinary biomarkers (UcGMP andUcGMP to Urinary Creatinine ratio) will be collected. Values and the change from baseline for each biomarker will be summarized by visit, treatment group and open-label sacubitril/valsartan. Analyses will be based on the FAS.

[figure not shown]
These and other selected biomarkers to be studied will be those believed to be relevant to the pathophysiology of heart failure, including those related to cardio-renal or vascular function, injury and/or fibrosis/remodeling. Biomarkers may include ones assessing cardio-renal or vascular benefit or ones related to the study drug mechanism of action. The list of blood and/or urine biomarkers may change during the course of the study as new or more relevant biomarkers are determined. Biomarker analysis may also occur retrospectively after study close with biomarker decisions dependent on study outcome and/or new biomarkers relevant to this heart failure patient population.

[figure not shown]
Biomarker values will be based on clinical laboratory samples processed and assessed by the central laboratory. Values below the limit of detection (LOD) (i.e., indicated as <LOD) will be converted to (0.5)(LOD) for purposes of analysis. Values indicated as 'Reported and Unreliable' will be excluded from analysis.

[figure not shown]
Biomarker samples from patients who withdrew consent will not be analyzed by the central laboratory.

BNP samples, which were originally assayed using P100 tubes, will be re-assayed using EDTA tubes for purposes of a side-by-side comparison of results where the value and change from baseline at each visit will be summarized for the subset of patients who have change from baseline values for the two BNP assays at the given visit.

Additional analysis of biomarkers is discussed in Sections 2.7 and 2.13.

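### Secondary objective 3 asks how the drugs compare on the Zc-biomarker relation, but the visible SAP 2.7.2 plans only per-arm and pooled correlations and no between-arm estimate

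*SAP*

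**What the plan says.** The objective is comparative. SAP 1.2 states it as "To evaluate the effect of sacubitril/valsartan vs. enalapril after 4 weeks of treatment on the relation between the change in aortic characteristic impedance" and the change in biomarkers. Protocol 2.2 and the protocol summary word it the same way.

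The method is not. Protocol 9.5.1 says that correlation coefficients "during both trough and 4 hours post-dose at Week 4 will be calculated by treatment and overall". SAP 2.7.2 keeps these for changes from baseline, which "to Week 4 trough will be calculated by treatment and overall. Corresponding two-sided 95% confidence intervals and p-values will be provided", and applies the same analysis to changes from trough to 4 hours post-dose. The biomarkers are BNP, UcGMP and the UcGMP to urinary creatinine ratio. On-treatment versions of all secondary analyses are added.

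The other two secondary objectives open with the same versus-enalapril wording and do get a contrast. For NT-proBNP, SAP 2.7.2 specifies "The estimated treatment effect in terms of ratios of geometric means, based on the least squares means from the ANCOVA model". The echocardiographic measures get an ANCOVA with treatment and baseline.

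Two more passages matter. SAP 2.6 says "There is no key secondary objective". SAP 2.12 ends: "Additional analysis of biomarkers is discussed in Sections 2.7 and 2.13". Section 2.13 is blacked out.

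**The concern.** A correlation within one arm describes that arm. The overall correlation pools the arms. Neither estimates how the relation differs between the drugs, which is what objective 3 asks. The intervals and p-values that the SAP adds belong to each coefficient. The natural reading is that each p-value tests its coefficient against zero, although the SAP does not spell this out.

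If the plan is followed exactly as visible, objective 3 ends with two columns of correlations and no answer to its own question. The obvious shortcut is then to note that a correlation is significant in one arm and not in the other. That pattern is common when the true correlation is the same in both arms, so it cannot stand in for a contrast.

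**Working it through.** **1. Text side by side.**

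| Secondary objective | Comparative wording | Between-arm estimate in the visible text |
|---|---|---|
| 1. NT-proBNP | yes | yes: ratio of geometric means from ANCOVA |
| 2. Echo measures | yes | yes: ANCOVA with treatment |
| 3. Zc-biomarker relation | yes | none |

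Protocol 9.5.3 only points back to 9.5.1. SAP 5.5 writes out models for the primary and NT-proBNP analyses only. SAP section 4 lists no added contrast for objective 3.

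**2. The plan's own figures.** SAP section 3 sizes the trial "accounting for a dropout rate of 20% from first visit to subsequent follow up and a 10% rate of non-evaluable data". With SD 80, difference 30, two-sided 0.05 and 90% power, a t-test needs 151 per arm; 151/0.70 = 215.7, so 216 per arm and 432 in total, as stated. For NT-proBNP, 172 per arm with log difference 0.288 and SD 0.85 gives 88.1% power, against the stated 88%. Both reproduce. Neither concerns objective 3, for which the documents give no power, precision or expected correlation.

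**3. Evaluable patients per arm (assumption: the design loss rates apply at Week 4).**
- 432 x 0.70 / 2 = 151
- 432 x 0.80 x 0.90 / 2 = 155 (rounded down)
- 432 x 0.80 / 2 = 173 (20% dropout only)

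**4. Precision of a between-arm contrast.** This assumes Pearson correlation and bivariate normality. The SE of the Fisher z difference is sqrt(2/(n-3)), the half-width is 1.96 x SE, and the difference detectable with 80% power is 2.80 x SE. The last column is power for r = 0.1 vs 0.3, that is atanh(0.3) - atanh(0.1) = 0.209.

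| n per arm | SE | Half-width | 80% power for | Power, 0.1 vs 0.3 |
|---|---|---|---|---|
| 151 | 0.116 | 0.228 | 0.326 | 44% |
| 155 | 0.115 | 0.225 | 0.321 | 45% |
| 173 | 0.108 | 0.213 | 0.304 | 49% |

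**5. Why per-arm p-values cannot replace it.** Let both arms share the same true r, and let p be the per-arm power from Fisher z with SE 1/sqrt(n-3). Then P(exactly one arm significant) = 2p(1-p). For n = 151 and r = 0.10, p = 0.231 and 2 x 0.231 x 0.769 = 35.5%.

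| Assumed r in both arms | n = 151 | n = 155 | n = 173 |
|---|---|---|---|
| 0.05 | 16.9% | 17.1% | 18.0% |
| 0.10 | 35.5% | 36.0% | 38.3% |
| 0.15 | 49.5% | 49.7% | 50.0% |
| 0.20 | 42.5% | 41.6% | 37.2% |
| 0.25 | 22.0% | 20.7% | 15.6% |
| 0.30 | 6.9% | 6.1% | 3.7% |

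Simulation (40,000 trials per case, n = 151 and 173, r = 0.10 to 0.20) agrees. There the Fisher z contrast rejects in 5.0 to 5.2% of all trials, and in 10 to 13% of those with exactly one significant arm.

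Example with n = 151 per arm: observed r of 0.18 and 0.14 give p = 0.027 and p = 0.086. The z difference is 0.04, 95% CI -0.19 to 0.27.

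**6. A limit of the Fisher z difference.** Suppose both arms have the same Zc-biomarker slope and the same residual SD, but one arm's biomarker changes have k times the SD. Then r²/(1-r²) is multiplied by k². From r = 0.20, where r²/(1-r²) = 0.0417:
- k = 1.5 gives 0.0417 x 2.25 = 0.094, so r = 0.29 and a z difference of 0.10
- k = 2 gives 0.0417 x 4 = 0.167, so r = 0.38 and a z difference of 0.20

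A difference in correlations can therefore appear with no difference in slope. Unequal spread is plausible here, because protocol 1.1 says that neprilysin inactivates natriuretic peptides.

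**The case against.** The strongest objection is that the absence is shown only for the visible text. Beyond the pointer to 2.13, item 18 of the SAP change log, which clarifies these same Week 4 correlation analyses, lists a blacked-out section beside 2.7.2. The protocol's contents list also has a blacked-out entry between 9.5.3 and 9.7. None of this shows that a contrast exists, but it rules out saying that the plan as a whole lacks one. This objection stands and lowers confidence.

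The second objection is that little is lost. Coefficients with 95% CIs appear side by side, and a reader with r and n per arm can compute the Fisher z difference. That is true, and it is one reason for the low priority. A difference derived afterwards, however, has no coefficient, scale or estimator fixed in advance. There are three biomarkers and two intervals, so six comparisons, or twelve with the on-treatment repeats. The slope difference cannot be recovered from correlations alone.

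The third is that the table in step 5 is generic: 2p(1-p) peaks at 50% for any two-group report, and the correlations are assumed. This also stands. The conditional figure of 10 to 13% likewise holds only for r = 0.10 to 0.20; by simulation it is 20 to 22% at 0.05, 18 to 20% at 0.25 and 31 to 38% at 0.30. Evaluable n could also fall below 151, because each correlation needs paired Zc and biomarker values and SAP 2.12 excludes biomarker results flagged as unreliable.

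A reader might infer that the sponsor means to judge the drugs by which arm reaches significance. No passage says so. The risk comes from what is left unstated.

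**Conclusion.** The mismatch between objective and method is real in the visible text: a comparative secondary objective has no stated comparison, and the two objectives beside it do. Confidence is moderate because of the redactions.

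Priority is low. There is no key secondary objective, and objective 3 carries no power claim. It would be wrong to infer that the trial's main result is at risk, since the primary ANCOVA does not depend on these correlations. It would also be wrong to read 35 to 50% as an error rate of this trial. It is an illustration for an assumed common r of 0.10 to 0.20, and it falls to 4 to 7% at 0.30.

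The precision figures rest on the design loss rates holding at Week 4, and on Pearson correlation with bivariate normality. The SAP does not name the coefficient.

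**What to change.** In SAP 2.7.2, for each of the three biomarkers and for both the baseline-to-trough and the trough-to-4-hour changes:

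1. Name the correlation coefficient and the scale of the biomarker change. NT-proBNP is analysed on the log scale; the correlation paragraph gives no scale.
2. Report one prespecified between-arm estimate with a 95% CI. It can be the treatment-by-biomarker-change interaction (difference in slopes) in a regression of Zc change. Or it can be the difference in Fisher z-transformed correlations, with a note that it also reflects each arm's spread of biomarker change.
3. State that it is read as an estimate and not as a pass/fail test, and that per-arm p-values are not used to compare the drugs. Keep the per-arm correlations.

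If 2.13 already contains the contrast, a cross-reference from 2.7.2 is enough. Rewording objective 3 as a descriptive within-arm association would also remove the mismatch, but it leaves the drug comparison unanswered although the data are collected.

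The cost is SAP wording and a short calculation on data already collected, with no new visits or samples. The downside is the modest precision: the interval will often be too wide to settle the question, and the report should say so.
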